## **4. OBJECTIVE(S)/SPECIFIC AIMS AND HYPOTHESES**

- *A concise statement of the goal(s) of the current study.*
- *The rationale for and specific objectives of the study.*
- *The goals and the hypothesis to be tested should be stated.*

The goal of the Roybal Center for Personalized Trials is to focus on innovative, behavioral interventions aimed at promoting and improving the overall health and well-being of older adults through the conduct of fully powered, meaningful, personalized trial pilots. The goal of this project is to evaluate the effects of a combined Mind-Body Intervention on increasing sleep duration in middle aged women working in health care, and to determine which intervention component proved most effective for each individual participant

Thus, the aims of this pilot study are :

**Primary Aim:** Determine if a personalized trial testing a Mind-Body Intervention (MBI) can produce a meaningful increase in the average daily sleep duration among women 40 – 60 years of age working in healthcare.

**Exploratory Aim 1:** Evaluate the effect of the MBI on sleep quality and other physiological factors.

**Exploratory Aim 2:** Explore the role of anxiety and depression as a potential mediator between perceived stress and sleep quality before, during, and after the MBI.

## 5. RESOURCES AVAILABLE TO CONDUCT THE HUMAN RESEARCH

- *Explain the feasibility of meeting recruitment goals of this project and demonstrate a potential for recruiting the required number of suitable subjects within the agreed recruitment period*
  - *How many potential subjects do you have access to?*
- *Describe your process to ensure that all persons assisting with the trial are adequately informed about the protocol and their trial related duties and functions*

We have planned for a broad base of recruitment efforts to potentially recruit a diverse representation of this population.

Northwell employs over 79,000 individuals with strong representation by women in clinical, clerical, and administrative capacities. Northwell employs more than 19,000 nurses. National statistics report that 90.6% of nurses are women and that the average age of a nurse in 2021 was 52 years of age. We believe we have an adequate population from which to recruit up to 65 participants for this study

Institute of Health System Science staff must meet certain eligibility criteria before assisting with this pilot study. All staff members must be listed on the IRB protocol submission and be up to date with trainings and attestations as required by the Northwell Health Human Research Protection Program. Additionally, staff will be required to participate in biweekly meetings with the Principal Investigator, and an additional weekly meeting with the Project Manager, in order to stay informed about the study protocol, staff duties and functions, and to answer any questions that come up within the group. Staff will have daily access to the Project Manager, Director of Clinical Research, and Principal Investigator to answer any protocol questions they may have outside these established weekly meetings.

## 6. RECRUITMENT METHODS

- *Describe the source of potential subjects*
- *Describe the methods that will be used to identify potential subjects*

- *Describe any materials that will be used to recruit subjects. A copy of any advertisements (flyers, radio scripts, etc.) should be submitted along with the protocol.*
- *If monetary compensation is to be offered, this should be indicated in the protocol*

Since the proposed study will take place virtually, potential participants are not required to reside within travelling distance of Northwell Health.

Potential participants will be recruited via the following avenues:

- E-mail advertisement through Northwell employee communication channels
- E-mail advertisement through existing email lists from those who have previously expressed interest in participation in a Personalized Trial or who have screen failed for other Institute-led research, but who have been informed their data will be retained for future research.
- Online research listings, such as the Feinstein Institutes for Medical Research clinical trials listing (<https://www.northwell.edu/clinical-trials>) and ClinicalTrials.gov (<https://www.clinicaltrials.gov/>)
- Recruitment posts on Northwell Health Facebook page
- Electronic and social media communications serving Northwell affiliates
- 

Potential participants will self-identify as having a minimum threshold of poor sleep duration over the last 3 months and interest in participating in a Personalized Trial.

Participants will be able to keep their Fitbit activity tracker (value \$150) as compensation for participation in the baseline period. Additionally, participants who are 80% compliant with Fitbit wear and survey responses are eligible for a weekly lottery (\$50 award). Adherent participants are eligible to win a maximum of eight times (\$400) during the 14 week intervention and follow-up periods. Upon completion of all study activities, participants will receive a \$50 clincard.

## 7. ELIGIBILITY CRITERIA

- *Describe the characteristics of the subject population, including their anticipated number, age, ranges, sex, ethnic background, and health status. Identify the criteria for inclusion or exclusion of any subpopulation.*
- *Explain the rationale for the involvement of special classes of subjects, such as fetuses, pregnant women, children, prisoners or other institutionalized individuals, or others who are likely to be vulnerable. You cannot include these populations in your research, unless you indicate such in the protocol*

- *Similarly, detail exclusionary criteria: age limits, special populations (minors, pregnant women, decisionally impaired), use of concomitant medications, subjects with other diseases, severity of illness, etc.*

Up to 65 participants will be randomized to receive this pilot study protocol. We aim to recruit a diverse pool of participants with varied ethnic and racial backgrounds.

Inclusion:

- Age 40 – 60 years
- Sex assigned at birth-female
- Northwell employee or affiliate
- Self-reported history of short sleep duration (<7h per 24-h period) for at least 3 months
  - After a 2-week run-in, Fitbit verified short sleep duration, and ≥80% adherence of Fitbit wear and survey submission
- Self-report of perceived stress ≥18 using the Perceived Stress Scale (PSS)
- Owns and can regularly access a smartphone capable of receiving text messages
- Owns and can regularly access an e-mail account
- Willingness to wear a Fitbit device

Exclusion:

- Age < 40 or > 60 years old
- Sex assigned at birth- male
- Not a Northwell employee
- No history of short sleep duration or non-adherent to the Fitbit wear and survey submission
- Self report of perceived stress <18 using the Perceived Stress Scale (PSS)
- Women who are pregnant or breastfeeding
- Does not own or cannot regularly access a smartphone capable of receiving text messages
- Does not possess or cannot regularly access an email account
- Deemed unable to complete the study protocol as a result of cognitive impairment, severe medical or mental illness, or active or prior substance abuse
- Planned surgeries within 6 months from study start date
- Participants who have been previously told by a clinician they have mobility limiting health conditions and/or not to engage in walking for 30 minutes, three times per week or yoga

Planned travel outside the United States within participant's intervention period will be determined on a case-by-case basis so as not to exclude interested and able participants from enrolling in the study.

Since this study will take place virtually, potential participants are not required to reside within travelling distance of Northwell Health. Therefore, the exclusion criteria do not preclude those living outside of New York State from passing

screening. Individuals who reside outside New York State will be recruited after there is an awareness of applicable human research protection laws that may apply to the research. Individuals who do not live in a reviewed state will have their enrollment workflow paused and may be removed from the waitlist if their state is reviewed in the future and provided there are no HSP laws that preclude their enrollment. In that instance, the protocol and/or consent form may require revision to meet the state of interest's requirements.

## 8. NUMBER OF SUBJECTS

- *Indicate the total number of subjects to be accrued locally. If applicable, distinguish between the number of subjects who are expected to be pre-screened, enrolled (consent obtained), randomized and complete the research procedures.*
- *If your study includes different cohorts, include the total number of subjects in each cohort.*
- *If this is multisite study, include total number of subjects across all sites.*

Up to 1000 potential participants may be screened for study eligibility. Up to 65 participants will be randomized until 60 (30 participants in each arm) complete research procedures with any data (Fitbit or survey) post- randomization. Eligible participants will be randomized (1:1) into Arm 1 or Arm 2. In Arm 1 (N=30), participants will receive a personalized intervention comprised of three components delivered in a ABCCBA sequence over a total period of 12 weeks, where A- mindfulness, B-yoga, and C-guided walking. During each 2-weeks block, participants will be prompted to complete 3 x 30-minute intervention sessions weekly. In Arm 2 (N=30), participants will receive a personalized intervention comprised of the same three components delivered in a CBAABC sequence over a total period of 12 weeks. Prompts will be delivered weekly to Arm 2 as well.

[figure not shown]
## 9. STUDY TIMELINES

- *Describe the duration of an individuals participation in the study*
- *Describe the duration anticipated to enroll all study subjects*
- *The estimated date of study completion*

The study will take place over the course of 16 weeks. Participants will begin the trial with a 2-week run-in period during which their baseline sleep duration and adherence to the Fitbit wear and survey submission will be assessed. Following the 2-week run-in period, participants deemed eligible and achieved at least 80% adherence of Fitbit wear and survey submission will be randomized to one of the two intervention arms. Interventions will be delivered by a virtual link to online videos recorded by an experienced Zeel wellness provider. Participants will be limited to three views of the study-provided intervention content each week. During the intervention participants will be asked to wear their

Fitbit device each *day and night*. They will also complete sleep diaries and have their physiological factors assessed using Fitbit devices each day. Participants' perceived stress will be measured using the ecological momentary assessment (EMA); screening for anxiety and depressive symptoms will be assessed using the patient health questionnaire (PHQ-4), a self-report version of the Primary Care Evaluation of Mental Disorders (PRIME-MD). Both EMA and PHQ-4 will be evaluated pre-intervention, bi-weekly during the intervention, and post-intervention. After 12 weeks of receiving the MBI, participants will enter the two-week follow up period to allow for a personalized report of their observed data to be generated.

Fig1. Trial Design

Potential participants will have the opportunity to provide preferences of start dates during their enrollment process. The study team will confirm applicability of the chosen start dates before confirming with a participant, so that no more than 20 potential participants will begin their baseline period on the same day and every baseline period begins on a Monday. Leading up to baseline start date, participants will receive messages from the study team with instructions preparing them for the study, including setting up their Fitbit devices and reminding them of their upcoming start date. Enrollment will be ongoing until 60 participants have been randomized and provide any data post-baseline. We estimate that the final participant will be randomized by September 30, 2023, and data collection will cease by January 15, 2024.

## 10. ENDPOINTS

- *Describe the primary and secondary study endpoints*
- *Describe any primary or secondary safety endpoints*

This study is a minimal risk pilot whose primary objective is to assess a meaningful increase in the average sleep duration of women 40 – 60 years of age working in healthcare.

## 11. RESEARCH PROCEDURES

- *Include a detailed description of all procedures to be performed on the research subject and the schedule for each procedure.*

- *Include any screening procedures for eligibility and/or baseline diagnostic tests*
- *Include procedures being performed to monitor subjects for safety or minimize risks*
- *Include information about drug washout periods*
- *If drugs or biologics are being administered provide information on dosing and route of administration*
- *Clearly indicate which procedures are only being conducted for research purposes.*
- *If any specimens will be used for this research, explain whether they are being collected specifically for research purposes.*
- *Describe any source records that will be used to collect data about subjects*
- *Indicate the data to be collected, including long term follow-up*

Potential participants who self-identify as having poor sleep duration (<7 hrs per 24hrs) will be directed to a study information site with details about the pilot study. Those who are interested in participating in this pilot study will be directed to sign a HIPAA Authorization form before completing an initial screening survey process. The HIPAA Authorization will be electronically signed via RedCap. The initial screening process includes questions pertaining to inclusion and exclusion criteria and administration of the Perceived Stress Scale (PSS). Consenting coordinators will review these data and determine whether a potential participant is eligible to participate. Those who are eligible will receive a link to a short video about key details from the consent form, as well as an electronic copy of the consent form. Potential participants will also be given the option to set up a 30-minute phone call with a research coordinator, where the research coordinator will describe the study process and offer an additional opportunity for the potential participant to ask any questions. After completing or opting out of the phone call, the potential participant will be sent a link to view and electronically sign the consent form in RedCap. Before being able to sign and submit the consent form, potential participants must demonstrate their understanding of the protocol by correctly answering 4 questions pertaining to the information presented in the consent form.

This study is funded by the National Institute of Aging (NIA) and a requirement of funding is to collect extensive demographic data during the screening process (prior to consent) on eligible participants, and to report this data to the NIA monthly on an individual level by study ID. The intended aim of this requirement is to ensure that funded projects are enrolling diverse populations and that screening does not systematically exclude members of underrepresented groups. These questions have been separated out from demographic data pertinent to the study aims and participants are informed in both the consent and on the study document that they have the option to decline responding to the questions without jeopardizing their ability to participate in the study.

Once potential participants successfully submit their signed consent form, they will receive an onboarding questionnaire to collect more information, including a home address. A Consenting Coordinator will review this information and send the potential participant a message which will include a confirmation of the start date

of their baseline period, and information about what to expect during onboarding to the study. They will receive an initial study kit including a Fitbit device via mail and will receive a copy of their electronically signed HIPAA authorization and consent form with a URL to view the informed consent video that they watched previously.

All baseline periods will begin on a Monday. The baseline period will take place over the course of 2 weeks. Participants will be instructed to continue treating their sleep quality issues as they normally would and not to participate in yoga, mindfulness exercises or walking bouts.

Each morning, baseline participants will receive a survey asking a few questions about their sleep quality the previous night using a modified version of the Consensus Sleep Diary, as well as factors that may have contributed to any sleep issues

During the baseline period, potential participants will be asked to wear their Fitbit all day and night, even while they are sleeping. Participants will be asked to download the Fitbit app to their smart phone. Baseline participants will be instructed to sync their Fitbit device by opening the Fitbit app on their phone at least every two days and to charge their device at least every four days.

Ten days into the baseline period, a Consenting Coordinator will review individual adherence to Fitbit wear and survey responses. Adherence to Fitbit wear will be defined as recorded activity of greater than 12 hours a day, and recorded sleeping activity greater than 180 minutes in total. Survey adherence will be defined as submission of a given survey. Baseline participants who do not achieve at least 80% adherence of Fitbit wear and survey submission during the first 10 days of the baseline period will be given until day 14 of the trial to obtain 80% adherence. Those who still do not meet 80% adherence by day 14 will be withdrawn from the study. Those participants who do maintain at least 80% adherence during the baseline period will be randomized to one of two intervention sequences in the pilot study. Participants who are randomized to receive intervention sequences will receive confirmation including their protocol timeline. Enrollment will continue until up to 65 participants have been randomized overall, with the goal of reaching 60 participants who complete research procedures with any post-randomization data: 30 participants randomized to receive ABCCBA and 30 participants randomized to receive CBAABC.

Each intervention sequence is made up of six 2-week periods assigning yoga, mindfulness or guided walking. Participants will be limited to 3 (30 minute) intervention sessions each week. During all intervention weeks (12 weeks total), participants will be asked to continue wearing their Fitbit device each day and night. They will continue to receive EMA surveys bi-weekly with questions about their health such as pain, fatigue, concentration, confidence, mood, and stress at that current moment, as well as a daily morning text asking them to report on their

sleep duration and quality the previous night, using a modified Consensus Sleep Diary. At the end of each intervention period on Sunday evening (every two weeks), participants will also receive the PHQ-4 and Perceived Stress Scale (PSS). A study phone number and email address will be available as part of each survey to contact the study team if a participant is concerned about any side effects they are experiencing. Participants will be instructed to contact 911 or go to the nearest emergency room in the event of a medical emergency.

Participants may receive additional messages to those outlined above with important reminders about their protocol (e.g., transition to a new intervention period), or to remind participants to sync their data or charge their devices. We will send a maximum of 5 text message surveys per day during the study, as well as text messages of these reminders and other important study communications.

In the event of an unanticipated circumstance that temporarily prevents a participant from completing study activities (illness, injury, death in the family, travel, etc.), the participant will have the option of pausing their study to resume once their circumstance has been positively resolved.

Participants will complete remote data monitoring after they have gone through one baseline period (two weeks), 6 intervention periods (two weeks each), and two weeks of follow-up), or 16 weeks total. Alternatively, a participant may choose to withdraw from the study, or be withdrawn from the study by the research team. Upon completion of data monitoring, participants will be given instructions on how to un-link their Fitbit from the study account.

We will compile the self-reported data from questionnaires, side effects, health assessments such as pain, fatigue, concentration, confidence, mood, and stress assessments, as well as information from the Fitbit regarding activity (steps, heart rate, flights climbed and intensity) and sleep (duration, estimated sleep stages, sleep score) for each individual participant. We will analyze this data and create a summary report of the participant's observed data over the study period, in relation to the intervention components

The participant will be sent this report in an encrypted email by our study team. Participants will also be sent links to several online videos explaining the terms and data visualizations available in their summary report. These videos will be general to the template report and will not contain any individual results or health information.

After being sent their report, participants will be asked to complete a satisfaction survey and offered the option to participate in a virtual follow-up interview (such as a video call over Microsoft Teams) with a member of our study team to talk about their experience as a research participant in this study. Participants will be asked several questions about what it was like to participate in the study. Participants will also be asked about their opinion on Personalized Trials. All

interviews will be audio-recorded and transcribed via Microsoft Teams (or equivalent program) to ensure full capture of information provided during the discussion. Participants will be informed that the session will be recorded prior to initiating the interview. If the participant declines to be recorded, they may still participate in the interview and the study team will take notes of the conversation. Audio and transcription files will be stored securely on the PHI-approved SharePoint server. Data collected from the satisfaction survey and the virtual follow-up interview will be used to inform future Personalized Trials designed by the investigator.

Participants will be able to keep their Fitbit activity tracker (value \$150) as compensation for participation. Additionally, participants who are 80% compliant with Fitbit wear and survey responses are eligible for a weekly lottery (\$50 award) during the intervention and follow-up periods. Adherent participants may be selected a maximum of eight times (\$400) during the 14 week intervention and follow-up periods. Participants who complete all study activities will receive a \$50 clincard as compensation for their participation.

## 12. STATISTICAL ANALYSIS

- *Describe how your data will be used to test the hypotheses.*
- *State clearly what variables will be tested and what statistical tests will be used.*
- *Include sample size calculations.*
- *If this is a pilot study, state which variables will be examined for hypothesis generation in later studies.*

### **Sample size justification:**

The primary aim of this study is to evaluate the effect of a personalized MBI on increasing the average daily sleep duration in working at Northwell Health. A sample size of 30 participants per arm achieve 80% power to detect a minimum effect size of 0.7 expected by one of the three Aim 2 interventions. Calculations were based on GEE tests for repeated measures considering a total of 28 daily measurements (4 weeks) per intervention, at a significance level of 0.05. The within subject standard deviation  $\sigma$  is anticipated to be maximum 2h, with an auto-regressive AR(1) base correlation of 0.95 taken at two successive timepoints. Estimated effect size and correlation values were derived from a previous fatigue study that employed similar intervention/design and collected sleep duration as exploratory endpoint.

The **randomization schedule** will be set up by a member of the Institute of Health System Science data team and provided to the data analyst assigned to this trial.. Randomization will occur with a fixed seed value for the purposes of repeatability and auditability, and the list of participants will be split into two groups using a

random shuffle function that takes that seed as input. The order in which an individual becomes eligible for one of these randomizations will determine the placement given (i.e. the first person eligible will be randomized to the intervention order given to participant 1 and continue sequentially). Eligibility is obtained by a participant maintaining at least 80% adherence of survey response, Fitbit wear  $\geq 12$  hours a day 80% of days, and 80% sleep data  $\geq 180$  minutes available through the baseline run-in period. The data analyst will alert the research coordinator of the assigned randomization once a participant becomes eligible during the baseline run-in period. As this pilot is not blinded to study coordinators, this concealed allocation involving the data analyst alerting the study coordinator of intervention assignment will be used to prevent bias by blinding the sequence up until time of randomization.

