### **Analytical Plan**

**Primary Outcome** – Mean Within-Subject Difference in daily sleep duration during 3 treatment periods from baseline. Participant's sleep duration will be measured objectively using Fitbit devices and by self-reported questionnaires. The Fitbit devices will collect information continuously that will be stored in Fitabase, a secure, online portal. Participant sleep activity will be aggregated by day.

Analysis of Primary Outcome: The effect of the personalized MBI intervention on individual's sleep duration will be assessed in each arm separately. Individual changes in the average daily sleep durations between the run-in and each treatment period will be reported using mean (95% confidence intervals CIs). Bland-Altman plots will be constructed to visualize the agreement between the Fitbit reported and self-reported sleep duration. The effects of treatment on sleep duration will be assessed using generalized estimating equations (GEE) with an unstructured variance-covariance matrix for measures on the same day to that night's sleep. This model accounts for possible autocorrelation and linear trends between sleep duration across time. The GEE models will include time of day of treatment exposure (AM versus PM) as a covariate.

**Exploratory Aim 1 Outcomes** - Mean Within-Subject Difference in daily sleep quality and other physiological factors during 3 treatment periods from baseline. This aim will explore the effects of the personalized intervention on sleep quality components (sleep onset, sleep staging, and overall sleep score) and physiological factors (breathing/resting heart rate, heart rate variability (HRV) and physical activity). All these measurements will be recorded and aggregated daily by the Fitbit device.

Analysis of Exploratory Aim 1 Outcome: The effect of the personalized MBI intervention on individual's sleep quality and physiological factors will be assessed in each arm separately. Individual changes in the average daily sleep quality (e.g., score), heart rate and daily average number of steps between the run-in and each treatment period will be reported using means (95% CIs. GEE models will be employed to test the effect of the intervention of sleep quality and physiological factors.

**Exploratory Aim 2 Outcomes** – Mean Within-Subject Difference in perceived stress, anxiety and depression scores measured objectively during 3 treatment

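### The plan does not say which component, arm or test decides the Primary Aim, and it sets no multiplicity control

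*Combined protocol and SAP*

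**What the plan says.** Section 4 of the combined protocol and SAP states the Primary Aim as a meaningful increase in average daily sleep duration produced by an MBI. The project goal just above it calls the intervention combined. It adds a second purpose, finding the most effective component for each individual.

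Section 12, Sample size justification, says: "A sample size of 30 participants per arm achieve 80% power". The stated target of that calculation is one component, since the aim is to "detect a minimum effect size of 0.7 expected by one of the three Aim 2 interventions", and the test is made "at a significance level of 0.05". The method is given as: "Calculations were based on GEE tests for repeated measures considering a total of 28 daily measurements (4 weeks) per intervention". The standard deviation "is anticipated to be maximum 2h, with an auto-regressive AR(1) base correlation of 0.95 taken at two successive timepoints".

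Section 12, Analytical Plan, defines the primary outcome as "Mean Within-Subject Difference in daily sleep duration during 3 treatment periods from baseline". The effect on "sleep duration will be assessed in each arm separately". On reporting, the plan then adds: "Individual changes in the average daily sleep durations between the run-in and each treatment period will be reported". Means and 95% confidence intervals are to be given, and a GEE model assesses treatment effects.

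Neither section names a deciding contrast, a pooled two-arm test, a global test, a testing order, sidedness or a multiplicity adjustment. The label Aim 2 in the power sentence also does not fit, because the only Aim 2 in section 4 is the exploratory mediation aim.

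**The concern.** The aim, the powered effect and the analysis refer to three different things: the MBI as a whole, one component out of three, and each arm on its own. Three components in two arms give six component-versus-run-in comparisons. With no rule for choosing among them, the deciding result could be picked after the data are seen, and the 5% error rate would then not describe the claim being made.

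This matters beyond bookkeeping. Only the other two aims are labelled exploratory. Section 4 says the centre's pilots are meant to be fully powered, and section 23 says the data should support larger efficacy trials. A chance finding in one component or one arm could steer that later work.

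**Working it through.** **Step 1. The plan's own figure.** Inputs from section 12: 30 per arm, effect 0.7, 28 daily values, AR(1) 0.95, SD at most 2 h, alpha 0.05. I assume two-sided tests and a comparison of two independent time-averaged means. The variance factor f is the mean of the 28 x 28 correlation matrix, and n = 2f(1.960 + 0.842)²/d².

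- AR(1) 0.95 per day gives f = 0.654. With d = 0.7 in SD units, n = 2 x 0.654 x 7.85/0.49 = 21 per arm. Power at 30 is Φ(0.7/√(2 x 0.654/30) - 1.960) = Φ(1.392) = 91.8%.
- With 0.7 read as hours and SD 2 h, d = 0.35, so n = 84 per arm and power at 30 is 39%.
- Figures near 30 appear only when an input is changed. Exchangeable correlation 0.95 gives 31 per arm (79.4%). AR(1) 0.95 stretched over the whole 28 days gives 32 (78.1%). An omnibus test over 3 or 4 means with no gain from averaging gives 30 (about 80.5%).

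The stated 80% is therefore not reproduced from the literal inputs.

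**Step 2. Correlation of the contrasts.** Each component has 28 days and all three share one 14-day run-in (sections 8, 9 and 12). With independent days, the correlation between two contrasts is (1/14)/(1/14 + 1/28) = 0.667. With AR(1) up to 0.95 applied to ABCCBA or CBAABC, the pairwise values run from about 0.62 to 0.85.

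**Step 3. Chance of at least one false positive.** Per arm, p is the probability that at least one of three correlated normal statistics passes its cut-off, found by simulation over AR(1) 0 to 0.95. Over two independent arms it is 1 - (1 - p)².

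| Reading | Per arm | Both arms |
|---|---|---|
| Any component, two-sided 0.05, either direction | 9.9-11.2% | 18.8-21.1% |
| Same tests, false increases only | 4.9-5.6% | 9.6-10.8% |
| Any component, one-sided 0.05 | 9.3-10.5% | 17.7-19.9% |
| One joint test per arm at 0.05 | 5% | 1 - 0.95² = 9.75% |
| Upper limit, independent two-sided tests | 1 - 0.95³ = 14.3% | 1 - 0.95⁶ = 26.5% |

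A single two-sided 0.05 test has 5% in either direction and 2.5% for false increases. Under the any-component, either-arm reading with two-sided tests the inflation is about fourfold on both counts: 18.8/5 to 21.1/5, and 9.6/2.5 to 10.8/2.5.

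**Step 4. Power after adjustment, taking 80% at face value.** The non-centrality is 1.960 + 0.842 = 2.80. An unpooled single-arm test at 0.05/3 has Φ(2.80 - 2.394) = 66%, and at 0.05/6 Φ(2.80 - 2.638) = 57%. If the 80% is a one-arm figure, pooling both arms gives Φ(2.80 x √2 - 2.394) = about 94% for one component at 0.05/3. All three depend on an 80% that step 1 did not reproduce.

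**The case against.** The strongest reply is that no success rule of this kind is in the plan. A reader might infer from the power sentence that any one significant component wins, but that sentence only describes the effect assumed for sizing. The run-in comparisons are to be reported as individual changes with confidence intervals, which is estimation. The GEE step names no contrasts and fits one joint test per arm equally well; an omnibus test even comes close to the stated 30 per arm. Six primary tests is thus a reconstruction. This part of the reply stands, and it is why the error rates above are conditional.

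It is also right that a flat 20% risk of wrongly claiming benefit is too strong a reading. The aim is an increase only. Under two-sided tests the risk of a false increase is about half that figure, and a rate near 20% requires one-sided 0.05 tests. Sidedness is not stated.

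A further reply is that this is a pilot, for which component-level estimates are a declared goal. That lowers the stakes but does not settle the matter, since the same section refers to fully powered pilots and section 12 gives a power and a significance level for the primary aim. The joint-test reading does not close the gap either: it still leaves 9.75% if success in either arm suffices.

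**Conclusion.** The concern holds as a gap in the plan: the aim, the powered effect and the by-arm analysis do not line up, and nothing says which result decides. The size depends on a rule that the plan does not give. If any component in either arm counted, the two-sided error rate would be about four times that of a single test. With one joint test per arm and success in either, it would be about twice.

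These figures assume normal test statistics, correct GEE standard errors, independent arms and a run-in shared by all contrasts.

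Two stronger conclusions are not supported. The sample size cannot be called wrong, because the contrast, effect-size scale and sidedness are missing; it can only be called not reproduced. Nor can 66% or 57% be given as the trial's adjusted power, since both apply only to unpooled single-arm tests with 80% taken at face value.

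**What to change.** In section 12:

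1. Name one primary test that matches section 4: the average of the three components versus run-in, pooled over both sequences (n=60), at two-sided 0.05.
2. Then test the three components versus run-in, also pooled, with Holm at 0.05.
3. Keep by-arm results descriptive.
4. Restate power for the pooled primary contrast and for a pooled component at 0.05/3. Give the effect-size scale, the sidedness and the exact contrast, and correct the Aim 2 label.

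A joint test or a pre-stated order of tests would also control the error rate, but a joint test would not identify which component worked.

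The cost is SAP wording and one new power calculation. Component-level claims face a stricter threshold, largely offset by using all 60 participants. No new data are needed.
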